11.1.1 Treatment Relatedness

Relationship of AEs to CyPep-1 and/or pembrolizumab will be collected as not related, unlikely related, possibly related, probably related and definitely related. Following ICH-E3, the drug relatedness will be dichotomized as follows:

- Related: possibly related, probably related, and definitely related OR with missing relatedness (= worst-case),
- Not related: unlikely related, and not related.

11.1.2 Adverse Event Onset and Duration

AE start and end date will be imputed, as applicable, using rules provided in [APPENDIX 1. PARTIAL DATE CONVENTIONS](#).

Study day of AE start/end will be calculated based on rules provided in Section [8.4](#), where date of interest is the (imputed) AE start/end date, respectively.

AE duration (days) is calculated as follows:

- = *AE stop date – AE start date + 1 day*,
when both dates are completely known or could be imputed
- = *trial termination date – AE start date + 1 day*,

Statistical Analysis Plan

SMS-0571/CyPep-1

V3.0 Final

04-Jun-2024

when the AE start date is fully known or could be imputed but the AE is ongoing at the end of the trial: in this case the duration will be presented as “>x days” in listings rather than “x days”

- = *death date – AE start date + 1 day*,
- when the AE start date is fully known or could be imputed but the AE is not resolved at the time of death: in this case the duration will be presented as “x days” in the listing
- = missing,
- when the AE has resolved but with a completely missing end date.

AE duration and study day of AE start/end will only be included in listings.

11.1.3 Analysis

All AEs will be presented by cohort/arm and overall.

An overview table of treatment-emergent AEs (TEAEs) will be produced, including counts and percentages of subjects (n) and events (#AE) for:

1. TEAEs,
2. TEAEs related to any study treatment (CyPep-1 or pembrolizumab),
3. TEAEs related to CyPep-1,
4. Serious TEAEs (TESAEs),
5. TESAEs related to any study treatment (CyPep-1 or pembrolizumab),
6. TESAEs related to CyPep-1,
7. CTCAE grade 3 or higher TEAEs,
8. CTCAE grade 3 or higher TEAEs related to any study treatment (CyPep-1 or pembrolizumab),
9. CTCAE grade 3 or higher TEAEs related to CyPep-1,
10. TEAEs leading to any study treatment (CyPep-1 or pembrolizumab) discontinuation,
11. TEAEs leading to CyPep-1 discontinuation,
12. TEAEs leading to pembrolizumab discontinuation,
13. TEAEs related to any study treatment (CyPep-1 or pembrolizumab) leading to any study treatment discontinuation,
14. TEAEs related to CyPep-1 leading to CyPep-1 discontinuation,
15. TEAEs related to any study treatment (CyPep-1 or pembrolizumab) leading to pembrolizumab discontinuation,
16. TEAEs leading to CyPep-1 dose reduction,
17. TEAEs leading to pembrolizumab dose reduction,
18. TEAEs leading to CyPep-1 dose interruption,
19. TEAEs leading to pembrolizumab dose interruption,
20. TEAEs leading to study discontinuation,
21. TEAEs leading to study discontinuation related to any study treatment (CyPep-1 or pembrolizumab),
22. TEAEs leading to study discontinuation related to CyPep-1,
23. Dose limiting toxicities (for Phase I and Phase IIa Arms A and C),
24. Treatment limiting toxicities (only for Arm B),
25. Fatal TEAEs,
26. Fatal TEAEs related to any study treatment (CyPep-1 or pembrolizumab),
27. Fatal TEAEs related to CyPep-1.

Adverse events will be coded based on the MedDRA (version specified in the *Data Management Plan*) for reporting by SOC and PT. SOC will be ordered in accordance with the international agreed upon sort order for SOC followed by descending order of overall PT incidence within the SOC.

Subjects with PTs of “Cancer Pain” and “Tumour Pain” will be pooled for outputs under PT of “Cancer Pain”. Similar pooling will be applied for inconsistently reported injection site reactions; list of applicable AEs will be provided by Sponsor/Data Management/Medical Monitor and reviewed at the Data Review Meeting before the database lock. In listings, such AEs will be flagged as pooled for tables but presented with the PT reported on eCRF (i.e., no pooling will be applied for listings).

For summaries of TEAEs by SOC and PT, a subject will be counted once within an SOC, even if the subject experienced more than one TEAE within a specific SOC (likewise for PT). For summaries of TEAEs by CTCAE v5.0 grade, a subject will be counted at most once at each severity grade within a SOC and/or PT. A missing severity will be assumed to be Grade 3. A missing relationship will be assumed to be likely related unless the subject was never treated with the specific therapy. Summaries of TESAEs by SOC and PT will be handled in a similar manner as TEAEs. A missing seriousness assessment will be assumed serious.

Summaries of adverse events by SOC and PT will include the following types:

Statistical Analysis Plan

SMS-0571/CyPep-1
V3.0 Final
04-Jun-2024

1. TEAEs,
2. TEAEs by CTCAE grade,
3. TEAEs related to any study treatment (CyPep-1 or pembrolizumab),
4. TEAEs related to CyPep-1,
5. TESAEs,
6. TESAEs by CTCAE grade,
7. TESAEs related to any study treatment (CyPep-1 or pembrolizumab),
8. TESAEs related to CyPep-1,
9. CTCAE Grade 3 or higher TEAEs,
10. CTCAE Grade 3 or higher TEAEs related to any study treatment (CyPep-1 or pembrolizumab),
11. CTCAE Grade 3 or higher TEAEs related to CyPep-1,
12. TEAEs related to CyPep-1 by CTCAE grade,
13. TEAEs leading to CyPep-1 discontinuation,
14. TEAEs leading to CyPep-1 discontinuation by CTCAE grade,
15. TEAEs leading to CyPep-1 discontinuation related to CyPep-1,
16. TEAEs leading to study discontinuation,
17. TEAEs leading to study discontinuation by CTCAE grade,
18. TEAEs leading to study discontinuation related to any study treatment (CyPep-1 or pembrolizumab)
19. TEAEs leading to study discontinuation related to CyPep-1,
20. Dose limiting toxicities,
21. Treatment limiting toxicities (TLTs),
22. Fatal TEAEs by relatedness to any study treatment,
23. Pre-treatment AEs.

A summary of TEAEs by PT and CTCAE grade will also be presented for TEAEs and TEAEs related to CyPep-1. The summary will be sorted by the total incidence of the PT.

A comprehensive listing of all AEs will be provided for all subjects. In addition, the following listings will be provided for SAF subjects:

1. TEAEs related to CyPep-1,
2. TESAEs,
3. CTCAE Grade 3 or higher TEAEs,
4. TEAEs leading to CyPep-1 discontinuation,
5. TEAEs leading to study discontinuation,
6. DLTs,
7. TLTs,
8. Fatal TEAEs.

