8.1.3 Adverse Events

Analyses of AEs will be based on the SAF set. AEs will be coded according to CTCAE v5.0 (for severity) and the Medical Dictionary for Regulatory Activities (MedDRA).

The total number/incidence of AEs will be summarized, including the number of subjects with at least one AE and the number of unique AEs per cohort and overall. The number of AEs per

severity (CTCAE) and relation to trial drug will also be included and summarized per cohort and overall. Additionally, listings of AEs leading to treatment discontinuation, resulting in death, and according to maximum severity will be tabulated. The incidence DLT/TLTs will also be evaluated for each dose level, and for all subjects combined. SAEs will be summarized in a similar manner.

The number of subjects and the number of AEs will be tabulated by MedDRA system organ class and preferred term. AEs will also be tabulated versus worst severity and worst relationship to treatment. In this table, subjects with AEs will be identified by their subject number.

Vital signs and body weight, 12-lead ECG parameters, laboratory data (hematology, biochemistry, coagulation, urinalysis) will be summarized using descriptive statistics. Shift tables showing changes from baseline will be generated where appropriate.

Pre-treatment events occurring between first assessment at screening and first dose of CyPep-1 will be summarized separately.

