4.3 Changes from and Additions to the Clinical Study Protocol

The following additions to the Clinical Study Protocol were made in this SAP:

1. Characterization of potential hepatotoxicity was added.
2. Markedly abnormal criteria for vital signs added.
3. Section for Other exploratory analyses was added (including analyses of PK and toxicity and intratumoral dose concentration).
4. Sections on visit alignment were added.
5. itRECIST analyses for Phase I cohorts were added.
6. Analyses of overall survival by RMH and GRIM-scores and including/excluding subjects with adrenocortical carcinoma were added.

The following changes from Clinical Study Protocol were made in this SAP:

Not applicable, no discrepancies between SAP and Clinical Study Protocol.

5 Trial Objectives and Endpoints

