5.2 Endpoints

5.2.1 Primary Endpoints

- Type and number of adverse events (AEs) according to National Cancer Institute (NCI) – Common Terminology Criteria for Adverse Events (CTCAE) criteria v5.0, and additional safety parameters of CyPep-1 as monotherapy and in combination with pembrolizumab.
- Dose limiting toxicities (DLTs) and the maximum tolerated dose (MTD) for determination of RP2D of CyPep-1 as monotherapy and treatment-limiting toxicities (TLTs) of CyPep-1 in combination with pembrolizumab.

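### The SAP's adverse-event tables by grade count a subject at every grade experienced, and no planned table gives the worst-severity tabulation specified in the protocol

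*SAP*

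**What the plan says.** SAP section 11.1.3 gives two counting rules. For treatment-emergent AE (TEAE) summaries not split by grade, "a subject will be counted once within an SOC, even if the subject experienced more than one TEAE within a specific SOC", and the same applies to preferred terms (PTs). For summaries by CTCAE grade, "a subject will be counted at most once at each severity grade within a SOC and/or PT".

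The second rule governs the SOC/PT summaries by grade for TEAEs, CyPep-1-related TEAEs, TEAEs leading to CyPep-1 discontinuation and TEAEs leading to study discontinuation. It also reaches serious TEAEs by grade, since the SAP handles those in the same manner. A further output is announced, "A summary of TEAEs by PT and CTCAE grade will also be presented for TEAEs and TEAEs related to CyPep-1", with no other counting rule attached.

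Protocol section 8.1.3 asks for severity in three ways:
- At event level: "The number of AEs per severity (CTCAE) and relation to trial drug will also be included and summarized per cohort and overall".
- In a sentence on further outputs, AEs "according to maximum severity will be tabulated".
- At subject level: "AEs will also be tabulated versus worst severity and worst relationship to treatment".

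On changes from the protocol, SAP section 4.3 records: "Not applicable, no discrepancies between SAP and Clinical Study Protocol".

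**The concern.** The type and number of AEs by CTCAE is a primary endpoint in both documents, so these tables report a primary result. Readers of an oncology safety table usually take the grade rows as a partition: each affected subject sits in one row, at the worst grade, and the rows add up to the subjects affected. Under the SAP rule they do not.

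Overlap is plausible here. CyPep-1 is injected repeatedly until confirmed progression, so local reactions can recur at different grades. SAP section 11.1.3 also pools inconsistently reported injection site reactions, and pools two pain terms, which places more events under one PT. SOC rows combine several PTs and can overlap further.

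The second part of the concern is that the protocol's worst-severity display is missing without being declared. Protocol section 8.1 requires changes known when the SAP is prepared to be described in it.

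**Working it through.** **Step 1. Look for a worst-grade AE table in the SAP.** In section 11.1.3, none of the 27 overview items, the 23 SOC/PT summaries, the PT-by-grade summaries or the listings is defined by maximum grade per subject. Worst-grade logic is used elsewhere: CTCAE shift tables (section 8.16), laboratory data (section 11.4) and ECOG shifts (section 11.5.4). None of these covers reported AEs.

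**Step 2. Compare with the protocol.** Section 8.1.3 specifies the worst-severity tabulation in addition to the number of AEs per severity. The SAP supplies per-grade subject counts but not the worst-severity table. The no-discrepancy statement in SAP section 4.3 is therefore incorrect on this point.

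**Step 3. Size of the overlap.** No figure in the plan needs reproducing, so what follows is an illustration. Take one PT reported at Grades 1 and 2 only. Let k be the number of subjects with the PT and b the number with both grades.
- SAP rule: Grade 1 row + Grade 2 row = k + b.
- Worst-grade rule: Grade 1 row + Grade 2 row = k.

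If both grades occur somewhere, k + b runs from max(2, k) to 2k.

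| k | SAP rule, sum of rows | Worst grade, sum of rows |
|---|---|---|
| 1 | 2 | 1 |
| 2 | 2 to 4 | 2 |
| 3 | 3 to 6 | 3 |
| 4 | 4 to 8 | 4 |
| 5 | 5 to 10 | 5 |
| 6 | 6 to 12 | 6 |

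**Step 4. Relate this to the documents' own data.** Protocol section 5.3.4 reports 12 related injection-site-pain events of Grade 1 and 2 at 5 mg/mL. The protocol synopsis (Arm A) gives 6 subjects in cohort 3. If those events all arose in cohort 3, at least one subject had the term more than once, since 12 / 6 = 2 events per subject even if all six were affected. The documents do not give k or b.

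Assume k = 6:
- b = 0: the rows sum to 6 (100%), and the two rules give the same table.
- b = 3, the other three with Grade 1 only: the SAP rule gives Grade 1 = 6 (100%) and Grade 2 = 3 (50%). Worst grade gives 3 (50%) and 3 (50%).
- b = 6: the SAP rule gives 6 (100%) and 6 (100%), which sum to 12 (200%). Worst grade gives 0 and 6 (100%).

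**The case against.** Several points on the other side stand.

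- **No direct clash of counting rules.** A reader might infer that the SAP rule contradicts the protocol outright. The protocol says worst severity is tabulated as well, asks for the number of AEs per severity, and nowhere forbids per-grade counting. The fault is an undeclared omission of a specified display.
- **The rows are not wrong in themselves.** A reader might infer that the low-grade rows are inflated or cannot be read as proportions of subjects. A subject with a Grade 1 and a Grade 2 event did have a Grade 1 event, so each row is a correct any-occurrence proportion. It exceeds a worst-grade row only because it answers a different question. What fails is adding the rows.
- **Severe toxicity is protected.** A reader might infer that high-grade incidence or the dose decision is distorted. Grade 3 or higher TEAEs have their own overview rows and SOC/PT tables, with each subject counted once per SOC and PT in the latter. DLTs, TLTs and fatal TEAEs are also reported separately. Dose Escalation Committee analyses fall outside this SAP (section 7.3).
- **Worst grade can be recovered.** The SAP plans a listing of all AEs, and the groups are small. This reduces the harm but does not replace the table.
- **The shells are unseen.** SAP section 4.2 places the table descriptions in a separate document, which might include a maximum-grade display. If so, the SAP text still does not provide for it.

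**Conclusion.** The point holds as an omission and a labelling problem in the reporting of a primary endpoint. The SAP's grade rows can overlap, the worst-severity tabulation in protocol section 8.1.3 is not provided for, and SAP section 4.3 wrongly reports no discrepancy.

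The effect is confined to the individual grade rows and any sum of them, including a sum of the Grade 3, 4 and 5 rows, which could disagree with the separate Grade 3 or higher table. Its size is unknown. In the illustration it runs from no difference to a doubling (6 to 12 counts for 6 affected subjects), on the assumption that all six cohort 3 subjects had the term. The documents show that overlap is possible, not that it occurred. The conclusion rests on the SAP text, since the table shells were not available.

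**What to change.** Preferred: replace the by-grade sentence in SAP section 11.1.3 with a rule that counts each subject once per SOC and once per PT, at the highest CTCAE grade reported within it. Apply it to all TEAE tables by grade, including the PT-by-grade summaries.

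Minimum: keep the present rule and add SOC/PT tables by maximum CTCAE grade per subject, for all TEAEs and for CyPep-1-related TEAEs.

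If any per-grade tables are kept, footnote them to say that the rows are not mutually exclusive and need not sum to the subjects affected, and list the departure in SAP section 4.3. Check the table shells against whichever rule is adopted.

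The cost is one SAP sentence or two added tables and a small programming change, with no new data. Replacing the rule loses the any-occurrence counts by grade, which are informative for recurrent low-grade injection reactions. Adding tables keeps them.

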11.2 Deaths

Deaths will be summarized for all SAF patients by cohort/arm and overall. The summary table will present the primary cause of death (target disease progression, study drug toxicity, study-specific procedure related incident, adverse event, non-study related incident, suicide, unknown, other [including specification]).

Deaths will also be listed for all patients in the SAF.

11.3 Pregnancies

No summary descriptive statistics will be produced, pregnancy test data will be presented in listings for all female subjects.

11.4 Clinical Laboratory Evaluation

Laboratory tests will be performed at times defined in the protocol Schedule of Assessments. Biochemistry, hematology, and coagulation parameters will be reported based on the International System of Units (SI). All clinical laboratory data collected during the on-treatment period will be presented for the SAF by visit, timepoint and cohort/arm, as applicable. Data collected during the pre-treatment and post-treatment periods will only be listed.

The following laboratory evaluations will be reported in data summaries:

1. **Hematology:** parameters to be assessed include hemoglobin, hematocrit, red blood cell (RBC) count, white blood cell (WBC) count with differential count (neutrophils, eosinophils, basophils, lymphocytes, monocytes), and platelet count. Neutrophil-to-lymphocyte count will additionally be derived.

Statistical Analysis Plan

SMS-0571/CyPep-1

V3.0 Final

04-Jun-2024

2. **Biochemistry:** parameters to be assessed include creatinine, alkaline phosphatase, phosphate, total bilirubin, direct bilirubin (only applicable if total bilirubin levels $> 1.5 \times \text{ULN}$ [upper limit of normal]), ALT (alanine transaminase), AST (aspartate transaminase), gamma-glutamyl transferase, total protein, albumin, uric acid, urea, sodium, potassium, calcium, chloride, glucose, lactate dehydrogenase, amylase, lipase, creatinine phosphokinase, cholesterol and triglycerides. Creatinine clearance will be estimated by the CKD-EPI and the Cockcroft-Gault formula.
3. **Coagulation:** parameters to be assessed include prothrombin time (PT), international normalized ratio (INR), and activated partial thromboplastin time (APTT).
4. **Urinalysis:** parameters to be assessed include leukocytes, nitrite, pH, protein, glucose, ketones, urobilinogen, bilirubin, occult blood (hemoglobin and erythrocytes) (dipstick). If abnormal, sediment will be performed (including WBC, RBC, epithelial cells, crystals, casts, bacteria, other).
5. **Thyroid function:** free T3, free T4, T3 and TSH.

Observed values and changes from baseline for hematology, biochemistry and coagulation laboratory evaluations will be summarized at each visit; maximum and minimum most extreme change will be summarized as well.

Urinalysis parameters will be summarized at each visit using the number (%) of subjects with results of normal; abnormal, not clinically significant; abnormal, clinically significant.

The number and percentage of subjects with NCI-CTCAE toxicities will be tabulated by laboratory evaluation with defined NCI-CTCAE grading at each visit and at any time (including unscheduled visits) for hematology, biochemistry, coagulation and thyroid function. Subjects with missing values post-baseline will be excluded from the summary. The denominator for percentages will be the number of subjects with at least one post-baseline assessment for the laboratory parameter in question.

Hematology, biochemistry, coagulation and thyroid function shift tables displaying the shift from baseline to the maximum value of NCI-CTCAE grade will be presented (see Section [8.16](#) for details on shift table creation).

Potential hepatotoxicity will be evaluated by presenting shifts from baseline to worst post-baseline NCI-CTCAE grade for ALT, AST, total bilirubin, alkaline phosphatase and gamma-glutamyl transferase split by baseline status (normal at baseline, abnormal at baseline). If any of the parameters of interest is abnormal at baseline, the subject is considered to belong to the abnormal at baseline group. Only subjects who have normal results for all parameters of interest are considered to belong to the normal at baseline group. NCI-CTCAE Grade 1 or above is considered abnormal for the purpose of this analysis.

Potential hepatotoxicity will additionally be assessed by similar table but splitting by liver metastasis at baseline (no metastasis, metastasis). Finally, a potential hepatotoxicity table by baseline liver metastasis and iRECIST best overall response (iCR + iPR + iSD or UPD + iCPD + NE) will be created.

Mean ($\pm \text{SD}$) hematology and biochemistry laboratory results will be plotted over time by cohort/arm for SAF. Parameters measured only before treatment start will be excluded from the plots.

Mean ($\pm \text{SD}$) ALT, AST, total bilirubin, and alkaline phosphatase results will be plotted over time for SAF by liver metastasis at baseline (no metastasis, metastasis) and separately by baseline result for parameter of interest (normal at baseline, abnormal at baseline; by parameter); subjects from all cohorts/arms will be pooled for this analysis (i.e., presenting only for Total: Phase I + IIa).

All laboratory parameters will be provided in subject data listings for all subjects, a separate listing including CTCAE Grade 3 or higher laboratory abnormalities will be created.

A table-listing of NCI-CTCAE graded lab data including the parameter name, CTCAE preferred term, clinical significance of assessment, worst severity and number of applicable events by subject, will be created for clinical chemistry, coagulation, hematology and thyroid function.

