6.1 General Study Design

This is a combined Phase I/IIa, open-label, dose escalation followed by dose expansion trial in subjects with advanced solid cancers. The trial consists of two phases and multiple arms, as shown in the diagram below ([Figure 1](#)).

Figure 1. Schematic trial design of Phase I (dose escalation, N=12) and Phase IIa (dose expansion Arm A, N=9 up to 18; combination Arm B, N=15; dose expansion liver metastases Arm C, N=9; and dose expansion melanoma Arm D, N=30)¹

For both phases and all trial arms, subjects will stay in the trial until end of trial or until confirmed disease progression, unacceptable toxicity, death or discontinuation for any other reason.

Phase I – dose escalation:

In this phase of the trial, safety and tolerability will be documented and the MTD/RP2D will be determined. Cohorts of 3 subjects will receive IT injections with CyPep-1. The DLT observation period for each dose level will be 6 weeks (5 weeks of trial treatment and 1 week of safety follow-up).

Screening will occur during the 4 weeks prior to start of CyPep-1 treatment.

In three dose cohorts of 3 subjects each, subjects will receive CyPep-1 IT at different concentrations (dose escalation) and volumes (depending on tumor size), i.e., 0.5 mg/mL, 2 mg/mL, or 5 mg/mL, respectively. These dose concentrations have been selected based on previous pre-clinical experience with CyPep-1.

Each subject will receive IT injection(s) with CyPep-1 on Day 1 of Weeks 1, 3, and 5, respectively. After each CyPep-1 administration, subjects will be required to stay at the clinic for at least 4 hours for safety and, for those in which PK will be assessed, also for PK monitoring. The data from the additional three subjects in cohort 3 will be used for further confirmation of RP2D. The following CyPep-1 administrations are planned as continuous Q2W administrations.

For each dose cohort, at least 24 hours must elapse between each subject to start treatment with CyPep-1. No intra-subject dose escalation is allowed.

¹ Note: as per sponsor confirmation letter from 14Apr2023, recruitment in Arm D was stopped after recruiting one subject due to recruitment difficulties. This SAP presents information regarding Arm D as presented in protocol v10.0/v10.1 (pre-dating the information letter).

Statistical Analysis Plan

SMS-0571/CyPep-1

V3.0 Final

04-Jun-2024

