8.15 Calculation of Percentages

All percentages will be calculated against the total number of subjects in the population with non-missing observations at the specific timepoint, unless otherwise noted in table footnotes.

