13.4 APPENDIX 4. VISIT ALIGNMENT

Mapping of protocol-defined visits into one common visit set for analysis purposes is presented below in [Table 10](#).

Table 10. Visit Alignment

Visit # (align.)	Visit Label (aligned)	Visit Day	Visit (per protocol)		
			Part I	Part IIa Arms A, B, C	Part IIa Arm D
1	Screening		SCREENING	SCREENING	SCREENING
2	Visit 1 Day 1	1	C1 D1	C1 D1	DAY 1
3	Visit 2 Day 8	8		C1 D8*	DAY 8
4	Visit 3 Day 15	15	C1 D15	C1 D15	DAY 15
5	Visit 4 Day 22	22		C1 D22	DAY 22
6	Visit 5 Day 29	29	C1 D29	C1 D29	
7	Visit 6 Day 36	36	C1 D36	C1 D36	
8	Visit 7 Day 43	43	C2 D1	C2 D1	
9	Visit 8 Day 50	50	C1 D50**		
10	Visit 9 Day 57	57	C2 D15	C2 D15	
11	Visit 10 Day 71	71	C2 D29	C2 D29	
12	Visit 11 Day 78	78	C2 D36	C2 D36	
13	Visit 12 Day 85	85	C3 D1	C3 D1	
14	Visit 13 Day 99	99	C3 D15	C3 D15	
15	Visit 14 Day 113	113	C3 D29	C3 D29	
16	Visit 15 Day 120	120	C3 D36	C3 D36	
17	Visit 16 Day 127	127	C4 D1	C4 D1	
18	Visit 17 Day 141	141	C4 D15	C4 D15	
19	Visit 18 Day 155	155	C4 D29	C4 D29	
20	Visit 19 Day 162	162	C4 D36	C4 D36	
21	Visit 20 Day 169	169	C5 D1	C5 D1	
22	Visit 21 Day 183	183	C5 D15	C5 D15	
23	Visit 22 Day 197	197	C5 D29	C5 D29	
24	Visit 23 Day 204	204	C5 D36	C5 D36	
25	Visit 24 Day 211	211	C6 D1	C6 D1	
26	Visit 25 Day 225	225	C6 D15	C6 D15	
27	Visit 26 Day 239	239	C6 D29	C6 D29	
28	Visit 27 Day 246	246	C6 D36	C6 D36	
29	Visit 28 Day 253	253		C7 D1	
30	Visit 29 Day 267	267		C7 D15	
31	Visit 30 Day 281	281		C7 D29	
32	Visit 31 Day 288	288		C7 D36	
33	Visit 32 Day 295	295		C8 D1	
34	Visit 33 Day 309	309		C8 D15	
35	Visit 34 Day 323	323		C8 D29	
36	Visit 35 Day 330	330		C8 D36	
37	Visit 36 Day 337	337		C9 D1	
38	Visit 37 Day 351	351		C9 D15	
39	Visit 38 Day 365	365		C9 D29	
40	Visit 39 Day 372	372		C9 D36	
41	Visit 40 Day 379	379		C10 D1	
42	Visit 41 Day 393	393		C10 D15	
43	Visit 42 Day 407	407		C10 D29	
44	Visit 43 Day 414	414		C10 D36	
45	Visit 44 Day 421	421		C11 D1	
46	Visit 45 Day 435	435		C11 D15	
47	Visit 46 Day 449	449		C11 D29	
48	Visit 47 Day 456	456		C11 D36	
49	Visit 48 Day 463	463		C12 D1	
50	Visit 49 Day 477	477		C12 D15	
51	Visit 50 Day 491	491		C12 D29	

Statistical Analysis Plan

SMS-0571/CyPep-1

V3.0 Final

04-Jun-2024

Visit # (align.)	Visit Label (aligned)	Visit Day	Visit (per protocol)		
			Part I	Part IIa Arms A, B, C	Part IIa Arm D
52	Visit 51 Day 498	498		C12 D36	
53	Visit 52 Day 505	505		C13 D1	
54	Visit 53 Day 519	519		C13 D15	
55	Visit 54 Day 533	533		C13 D29	
56	Visit 55 Day 540	540		C13 D36	
57	Visit 56 Day 547	547		C14 D1	

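### SAP 11.4 gives one ever-tested denominator for both any-time and by-visit laboratory toxicity percentages; for the visit rows this conflicts with SAP 8.15 and, taken literally, understates the rates

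*SAP*

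**What the plan says.** SAP 11.4 (Clinical Laboratory Evaluation) plans a table of the number and percentage of subjects with NCI-CTCAE laboratory toxicities "at each visit and at any time (including unscheduled visits) for hematology, biochemistry, coagulation and thyroid function". Two sentences on the calculation follow. The first reads: "Subjects with missing values post-baseline will be excluded from the summary". The second reads: "The denominator for percentages will be the number of subjects with at least one post-baseline assessment for the laboratory parameter in question". No separate denominator is given for the visit rows.

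SAP 8.15 (Calculation of Percentages) sets the general rule. All percentages are "calculated against the total number of subjects in the population with non-missing observations at the specific timepoint, unless otherwise noted in table footnotes". Section 11.4 does not refer to 8.15, and its rule stands in the body text rather than in a table footnote.

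Two other parts of the SAP matter here. Section 11.4 opens by stating: "All clinical laboratory data collected during the on-treatment period will be presented for the SAF by visit". Section 6.1 says that, in both phases and all arms, "subjects will stay in the trial until end of trial or until confirmed disease progression, unacceptable toxicity, death or discontinuation for any other reason". The aligned visit list in Appendix 4 runs at least to "Visit 56 Day 547".

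**The concern.** A subject tested at least once after baseline stays in the 11.4 denominator for every visit row. If that subject has left, or had no sample at that visit, the subject cannot appear in the numerator but is still counted below the line. In effect the row treats the subject as free of the toxicity at that visit.

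By-visit toxicity tables are there to show how laboratory toxicity develops over time. Safety and tolerability is a primary objective, and laboratory data fall under the additional safety parameters in the first primary endpoint (SAP 5.1.1 and 5.2.1). A denominator that stays fixed while the number sampled changes makes the visit rows hard to compare with one another. They would also not be comparable with other by-visit safety percentages, such as urinalysis in 11.4 and markedly abnormal vital signs in 11.5.1. Those state no denominator of their own and so fall under 8.15.

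**Working it through.** The documents state no figure on this point, so there is nothing to reproduce. The check compares the two rules.

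**Notation, for one parameter in one arm**
- N_any: subjects with at least one post-baseline value (SAP 11.4).
- n_v: subjects with a value at visit v (SAP 8.15).
- x_v: subjects with the toxicity at visit v.

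**Formulas**
- 11.4 read literally: x_v / N_any.
- 8.15: x_v / n_v.
- Ratio of the first to the second: n_v / N_any.

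Anyone tested at a post-baseline visit also belongs to N_any, so the ratio cannot exceed 1. The literal figure is correct only when every ever-tested subject is sampled at the visit; otherwise it is too low.

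**Where n_v falls below N_any**
1. *Later cycles.* Subjects leave at confirmed progression, toxicity, death or other discontinuation. The documents give no attrition rate.
2. *Days 8 and 22.* Appendix 4 lists these visits in the column for Arms A, B and C. Protocol 5.3.1.2 creates them in Arms A and B for the weekly schedule used with lesions above 7 cm, with assessments as on Day 15 apart from two central-laboratory samples. Subjects on the two-weekly schedule have no such visits. Here n_v is below N_any by design, before anyone has left.

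**Illustration, with assumed shares still tested**

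| n_v / N_any | Rate among tested | Shown under 11.4 read literally |
|---|---|---|
| 100% | 20% | 20% |
| 80% | 20% | 20% × 0.8 = 16% |
| 60% | 20% | 20% × 0.6 = 12% |
| 40% | 20% | 20% × 0.4 = 8% |
| 20% | 20% | 20% × 0.2 = 4% |

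**Whole-number example.** Arm B has 15 planned subjects; N_any = 15 and the counts below are assumed. One third of those tested have the toxicity at each visit.

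| Tested (n_v) | With toxicity (x_v) | 8.15: x_v / n_v | 11.4: x_v / 15 |
|---|---|---|---|
| 15 | 5 | 33.3% | 33.3% |
| 12 | 4 | 33.3% | 26.7% |
| 9 | 3 | 33.3% | 20.0% |
| 6 | 2 | 33.3% | 13.3% |
| 3 | 1 | 33.3% | 6.7% |

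The last row would also describe Day 8 if 3 of the 15 were on the weekly schedule and 1 of them had the toxicity.

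**Reading the exclusion sentence.** It does not say when a value must be missing. If it means missing at that visit, the visit rows agree with 8.15. If it means missing at every post-baseline visit, it only repeats the denominator sentence, and the dilution remains. The sentence that follows, with its requirement of at least one assessment, points towards the second reading but does not settle it.

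**The case against.** The strongest reply is that the SAP has not chosen the diluting denominator. Section 8.15 covers all percentages and allows exceptions only through table footnotes. Nothing in the SAP says that a specific section overrides it, and the exclusion sentence can be read visit by visit. The table descriptions and mock shells are separate documents that are not available here. This stands: what the documents show is two incompatible instructions, not a settled method. It does not remove the point, because a programmer building this table may well follow the sentence written for it.

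A reader might infer that late-visit rates will shrink towards zero and that cumulative toxicity will be hidden. The documents do not support that. They contain no attrition rate, and subjects with unconfirmed progression may stay on treatment until a confirmatory scan. The same table prints counts, and SAP 8.14 asks for the number of non-missing data points with categorical summaries. Late or worsening toxicity would also show in the any-time percentages, the worst-grade and hepatotoxicity shift tables, the mean plots over time and the Grade 3 or higher listing, none of which use this denominator.

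The scope is narrow too. After Cycle 1, protocol Tables 1b and 1d place hematology and biochemistry on Day 1 only, Table 1b has no coagulation row, and thyroid testing applies to Arm B only. Arm D stopped after one subject (SAP 6.1, footnote 1). No test, dose decision or expansion rule uses these percentages, and SAP 7.3 places the Dose Escalation Committee analyses outside the SAP.

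**Conclusion.** The point holds as an internal conflict between SAP 11.4 and 8.15 over the denominator for by-visit laboratory toxicity percentages. If 11.4 is applied as written, each visit percentage is multiplied by n_v / N_any, and the error is never upward. If 8.15 is applied, there is no error.

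The size in this trial cannot be derived. The shares tested, the toxicity rates and the Arm B counts used above are assumptions chosen to show the range. The direction does not depend on them, and for Days 8 and 22 the shortfall follows from the visit schedule whenever an arm contains any subject on the two-weekly schedule.

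The consequence is confined to descriptive visit rows. It is worth correcting before the tables are programmed, because two programmers could follow the same SAP and print different percentages.

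**What to change.** In SAP 11.4:

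- Keep the ever-tested denominator for the any-time rows only.
- For each visit row, divide by the subjects with a non-missing result for that parameter at that visit, as in 8.15, and show that n in the row or column header.
- Limit the exclusion sentence to subjects with no post-baseline value of the parameter, and tie it to the any-time rows.

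The mock shells should carry the same two denominators. The cost is a short SAP clarification and one change to the denominator in the table program. No additional data are needed.
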